### **High resolution computed tomography**

Change in total HRCT score and total parameter scores from initial scan to 24 weeks will be analyzed, using an ANCOVA model with baseline HRCT score as a covariate and treatment at screening as factors.

The same sensitivity and subgroup analyses as the primary may also be performed, if deemed necessary.

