### 3        Investigational plan

#### 3.1      Study design

Figure 3-1      Study Design scheme

This is a 32-week, subject- and investigator-blinded, randomized, placebo-controlled, parallel-group, non-confirmatory study to assess the clinical efficacy of ACZ885 administered subcutaneously (s.c.) in 6 injections given 28 days apart (Figure 3-1). The study will randomize approximately 38 patients (targeting 30 completers) with evidence of parenchymal involvement and histologically proven, chronic pulmonary sarcoidosis of  $\geq 1$  year duration with persisting activity at baseline despite background therapy as determined by clinical history, radiologic evidence (e.g. HRCT, MRI or chest x-ray), spirometry and MMRC dyspnea scale assessments. Randomization will be stratified by positive PET parenchymal tracer uptake (yes/no). Acceptable background therapy includes a stable regimen of prednisone  $\leq 15$  mg/day and/or no more than one immune suppressive agent (i.e., methotrexate, azathioprine, leflunomide or hydroxychloroquine).

Re-screening of subjects may be allowed with the consultation of the Sponsor's medical expert.

For each subject, there will be a maximum 40-day screening period. Screening is valid for 40 days from the time of the first screening assessment. [F-18]FDG-PET/CT scans obtained locally at the study site within 8 weeks of randomization will be acceptable for baseline assessment prior to receiving the first injection of ACZ885. However, any prior [F-18]FDG-PET/CT imaging must also have been done without changes in treatment during the subsequent period leading up to study randomization.

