Subjects who meet the eligibility criteria at screening will undergo evaluation of full baseline clinical and biomarker assessments prior to injection. Baseline assessments including safety laboratory evaluations and pulmonary function tests will not be available prior to dosing and for those measures eligibility criteria will be determined based on the screening results. Enrolled subjects will be randomized at a 1:1 ratio to receive treatment with either ACZ885 or placebo. On Days 1, 29, 57, 85, 113 and 141 patients will be administered s.c. dosing with ACZ885 at 300 mg or corresponding placebo treatment. All patients will return to the study center for safety and pharmacokinetic (PK) checks on an every four week basis at which time they will receive either study treatments depending on treatment arm. Additionally, patients will undergo clinical assessments that include pulmonary function tests with lung volumes, DLco, 6MWT, and clinical outcome assessments as outlined in the [Assessment Schedule](#).

At week 12, a second [F-18]FDG-PET/CT will be obtained. In addition, functional clinical measures Corporate Confidential Information will take place at this time point. The final dosing will take place on week 20, followed by a visit on week 24 Corporate Confidential Information

Corporate Confidential Information. Also included at the week 24 visit is the second HRCT assessment. Patients return for the end of study (EOS) visit at week 32.

A follow-up visit or phone call for SAEs must be performed 30 days following early discontinuation, or 8 weeks after last injection of study drug, whichever is later. If anaphylactic reactions occur after injection, two more immunogenicity samples (at the time of the event and 8 weeks later) need to be taken. Any patient who discontinues the study early will complete the Week 32, EOS visit. Patients discontinuing after week 12 will also undergo a second HRCT assessment at this visit, as assessed on a case-by-case basis by the Sponsor.

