#### 11.5.1.2 High resolution computed tomography (HRCT)

Change in HRCT scoring from initial scan to 24 weeks will be analyzed, using a regression model with baseline HRCT score as a covariate and treatment and PET positivity (yes/no) as factors. The HRCT scans will be evaluated using an HRCT scoring system quantifying various features such as: BVB: thickening or irregularity of the bronchovascular bundle; PC: parenchymal consolidation (including ground-glass opacifications); ND: intraparenchymal nodules; LS: septal and nonseptal lines; PL: focal pleural thickening; LN: enlargement of the mediastinal lymph nodes. The score for the lung will be determined using a scoring system similar to previous published literature ([Oberstein et al 1997](#); [Ors et al 2013](#)).

In addition, HRCT results will be evaluated for worsening, improvement, or stable outcome by 2 blinded assessors in side-by-side comparison. Results will be summarized in a shift table.

Corporate Confidential Information

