#### ***1.3.2. Secondary objective(s)***

Secondary objective(s)	Endpoints related to secondary objective(s)

To determine the effect of ACZ885 on decreasing the maximum standardized uptake value (SUVmax) [F-FDG-PET SUVmax in nodules (nodular uptake regions) after 12 weeks of treatment, compared to placebo

	

Percent change from initial scan in [F-FDG-PET SUVmax at week 12

To determine the effect of ACZ885 versus placebo on other parameters of pulmonary function testing (i.e., absolute FVC, FEV1, FEV1/FVC, FEV3, FEV6, FEF25-75, FEV3/FVC, 1- (FEV3/FVC), TLC, RV, RV/TLC, DLco and postbronchodilator FEV1/reversibility) in patients with

	

Lung function testing results at 24 weeks compared to baseline

sarcoidosis at 24 weeks compared to baseline	

To determine the effect of ACZ885 versus placebo on HRCT of patients with sarcoidosis at 24 weeks compared to initial HRCT scan as measured by side-by-side comparison by blinded reviewers and HRCT scoring

	

HRCT results at 24 weeks compared to HRCT initial scan measured by blinded reviewers and HRCT scoring

To determine the effect of ACZ885 versus placebo on the 6-minute walk test (6MWT) distance of patients with sarcoidosis at 12 and 24 weeks compared to baseline

	

6MWT results at week 12 and 24 compared to baseline

To determine the effect of ACZ885 on additional [F-18]FDG-PET outcomes (i.e., SUVmean, SUVpeak and volume of the lesions) after 12 weeks of treatment compared to placebo

	

Percent change from initial scan in additional [F-18]FDG PET outcomes at week 12

To assess the safety and tolerability of ACZ885 in patients with sarcoidosis as measured by adverse events (AEs)

	

Adverse events in patients taking ACZ885 compared to placebo

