### **6.1.5 Sensitivity analyses**

A sensitivity analysis will be performed on the primary endpoint adding PET positivity (yes/not) prior to randomization a factor. The same analysis as defined in Section 6.1.3 will be performed, and adding PET positivity as a covariate in the model.

A further sensitivity analysis may be performed using an LOCF imputation for missing values. The main purpose of this analysis will be the investigation of potential bias, caused by subjects excluded from the analysis due to prohibited concomitant medication use (as concomitant medication increase is primarily due to poor response). However, the analysis will not be restricted to these subjects. A summary of prohibited medication incidence (as defined by the Protocol Deviations database), will be produced which will present the number of subjects with COMD01 deviations and time to first COMD01 deviation by treatment group, this summary will serve to decide whether the LOCF analysis will be performed.

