### **6.2.3 Statistical model, assumptions and hypotheses**

#### **[F-18]FDG-PET/CT**

The mean percent change from baseline in SUVmax in the nodules at week 12 will be analyzed using ANCOVA with baseline SUVmax as a covariate and treatment as factor.

The same analysis as for the percent change from baseline in mean SUVmax in the nodules will be performed for the percent change from baseline in SUVmax in the lung parenchyma and the extra-thoracic regions, where available, at week 12. It will also be repeated for SUVmean in the parenchyma.

The percentage of patients with at least 50% reduction of SUVmax in nodules will be analyzed via logistic regression with baseline SUVmax as a covariate and treatment and PET positivity (yes/no) prior to randomization as factors.

The same sensitivity and subgroup analyses as the primary may also be performed, if deemed necessary.

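### SAP 6.2.3 misstates the factors of the HRCT ANCOVA: it dates treatment to screening, names one item under a plural, and drops PET positivity without explanation, unlike Protocol 11.5.1.2

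*SAP*

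**What the plan says.** For the change from initial scan to week 24 in the total HRCT score and the total parameter scores, SAP 6.2.3 (High resolution computed tomography) plans an analysis "using an ANCOVA model with baseline HRCT score as a covariate and treatment at screening as factors". It adds that the sensitivity and subgroup analyses defined for the primary endpoint may be repeated if thought necessary.

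Protocol 11.5.1.2 plans the HRCT analysis "using a regression model with baseline HRCT score as a covariate and treatment and PET positivity (yes/no) as factors".

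The objective in SAP 1.3.2 is "To determine the effect of ACZ885 versus placebo on HRCT of patients with sarcoidosis at 24 weeks", relative to the initial scan.

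On timing, Protocol 3.1 determines eligibility at screening and then states: "Enrolled subjects will be randomized at a 1:1 ratio to receive treatment with either ACZ885 or placebo". Dosing follows: "On Days 1, 29, 57, 85, 113 and 141 patients will be administered s.c. dosing". The same section stratifies randomisation by whether there is parenchymal PET uptake.

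**The concern.** The phrase about screening does not fit study drug. At that point a patient has at most stable background therapy (prednisone and/or one immune suppressant). The sentence therefore does not cleanly name the factor that carries the treatment comparison. It announces several factors and supplies one, and it omits a factor that the protocol lists for the same endpoint.

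The SAP says in section 1.1 that it describes how the protocol's planned analysis is implemented, yet the visible text gives no reason for this difference. If the sentence stays as it is, whoever programs the analysis must choose between a one-factor and a two-factor model. Protocol 6.4 allows the statistician, programmers and other sponsor staff to be unblinded at the interim analysis, so that choice could be made by people who have seen data by arm.

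**Working it through.** No figure in the plan is in dispute, so the main check sets the texts side by side.

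**1. Does study treatment exist at screening?** Screening lasts up to 40 days. Randomisation follows eligibility, and the first injection is on Day 1 (Protocol 3.1). Study treatment at screening is therefore none for every patient. Coding it literally for an illustrative 30 patients gives these design-matrix ranks:

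- intercept, baseline score, treatment at screening: rank 2 of 3, so the treatment term is not estimable;
- intercept, baseline score, study arm: rank 3 of 3;
- intercept, baseline score, study arm, PET positivity: rank 4 of 4.

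The literal wording cannot be run for study drug. Both natural repairs can.

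**2. Which repair does the text support?**

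| Analysis | Protocol section 11 | SAP section 6 |
|---|---|---|
| Percent predicted FVC (primary) | treatment by time, baseline by time, PET positivity | treatment by time, baseline by time; PET positivity only in a sensitivity analysis |
| SUVmax ANCOVA | baseline, treatment, PET positivity | baseline, treatment |
| 50% SUVmax reduction, logistic | baseline, treatment, PET positivity | baseline, treatment, PET positivity |
| HRCT change | baseline, treatment, PET positivity | baseline, then the phrase at issue; no PET positivity |

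The SUVmax sentence reads "using ANCOVA with baseline SUVmax as a covariate and treatment as factor", singular and without a time qualifier. The logistic sentence in the same section has two factors and a qualifier placing PET status before randomisation. The HRCT sentence has the plural and a time qualifier, which fits PET status and not treatment. That suggests lost words, but it is an inference.

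**3. Where else does PET positivity enter for HRCT?** SAP 6.2.2 gives descriptive summaries of HRCT total scores by PET positivity. SAP 6.1.5 specifies, for FVC: "A sensitivity analysis will be performed on the primary endpoint adding PET positivity (yes/not) prior to randomization a factor". For HRCT the same step is optional. SAP section 4 says the real stratum will be used where a patient was mis-stratified, but the HRCT model as written has no stratum term to which this could apply.

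**4. Size, for illustration.** Let R² be the share of the variance remaining after baseline score and treatment that PET positivity explains. Leaving it out multiplies the standard error of the treatment difference by about 1/√(1 − R²):

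- R² = 0.05: 1/√0.95 = 1.026
- R² = 0.10: 1/√0.90 = 1.054
- R² = 0.20: 1/√0.80 = 1.118

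The documents give no value for R², so 5-20% is an assumption.

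**5. Cost of including it.** With the 30 completers targeted in Protocol 3.1, and assuming all have both HRCT scans, residual degrees of freedom go from 30 − 3 = 27 to 30 − 4 = 26.

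**The case against.** A reader might infer that the SAP's HRCT model contains no ACZ885-versus-placebo term and so yields no information on the objective. The documents do not support that. The sentence does name treatment. The objective is explicitly ACZ885 versus placebo, the neighbouring ANCOVA uses treatment as its factor, and SAP section 4 defines treatment for analysis as the study treatment received. SAP 6.2.2 also requires listings and descriptive statistics by treatment and visit for secondary variables. Even on the literal reading, only the adjusted model estimate would be missing.

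The stronger counter-argument is that omitting PET positivity may be deliberate. The SAP also removes it from the primary model and the SUVmax ANCOVA, so an HRCT model with treatment alone would fit that pattern, with the words about screening left over from editing. This stands as a possible explanation, and it means the intended model cannot be read off with certainty. It does not answer the point: the SAP does not say so, the plural and the logistic model in the same section pull the other way, and the departure from Protocol 11.5.1.2 goes unexplained.

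It is also fair that this is one secondary endpoint in a study described as non-confirmatory, whose efficacy criterion rests on FVC alone.

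**Conclusion.** The concern holds as a specification defect. The arm comparison can be inferred from context; the factor set cannot. As written, the model departs from Protocol 11.5.1.2 and leaves the stratification factor to an optional sensitivity analysis.

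The main harm is an ambiguous prespecification. Any statistical loss would be in precision: the 3-12% larger standard error depends wholly on the assumed 5-20% of residual variance and should not be quoted as an estimate for this trial. Nothing here indicates bias in the HRCT comparison or affects the primary FVC criterion. The sentence should be corrected, but the defect does not threaten the trial's main conclusion.

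**What to change.** Rewrite the sentence in SAP 6.2.3 so that each HRCT score is analysed by ANCOVA with:

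- covariate: the baseline value of the HRCT score;
- factors: study treatment (ACZ885 versus placebo, assigned by the analysis-set rule in SAP section 4) and PET positivity (yes/no) prior to randomisation.

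This gives the factors of Protocol 11.5.1.2; the timing qualifier follows the SAP's own logistic model. Treatment should not be relabelled as randomised treatment, because Protocol 11.1 and SAP section 4 both analyse by treatment received.

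If leaving PET positivity out was intended, the SAP should say so, justify the departure from the protocol and name treatment as the single factor. Whether the primary and SUVmax models should also regain PET positivity is a separate question, best settled at the same time for consistency.

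The cost is one sentence and one degree of freedom, with no new data. It should be done before database lock and, where possible, before those choosing the model see HRCT results by arm.

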### **Key Pulmonary function tests (FEV1, FEV3 and FEV6)**

FEV1, FEV3 and FEV6 (both in liters and percent as units) will be analyzed using the same analysis as defined in Section 6.1.3 but under a frequentist approach (no prior will be applied). The same sensitivity and subgroup analyses as the primary may also be performed, if deemed necessary.

## **6.3 Exploratory objectives**

Corporate Confidential Information

## **7 Statistical methods for safety and tolerability data**

All subjects within the safety analysis set will be included in the safety data analysis.

### **7.1.1 Variables**

Adverse events, vital signs (blood pressure, pulse rate, body temperature), ECG intervals, laboratory measurements, immunogenicity, as well as subject demographics, baseline characteristics (including but not limited to PET disease assessment and MMRC dyspnea scale), and treatment information.

### **7.1.2 Descriptive analyses**

#### **Subject demographics and other baseline characteristics**

All data for background and demographic variables will be listed by treatment group and subject. Summary statistics will be provided by treatment group.

Relevant medical history, current medical conditions, results of laboratory screens, drug tests and any other relevant information will be listed by treatment group and subject.

#### **Treatment**

Data for study drug administration (rescue medication) and concomitant therapies will be listed by treatment group and subject.

#### **Vital signs**

All vital signs data will be listed by treatment, subject, and visit/time and if ranges are available abnormalities (and relevant orthostatic changes) will be flagged. Summary statistics will be provided by treatment and visit/time.

#### **ECG evaluations**

All ECG data will be listed by treatment, subject and visit/time, abnormalities will be flagged. Summary statistics will be provided by treatment and visit/time.

#### **Clinical laboratory evaluations**

All laboratory data will be listed by treatment, subject, and visit/time and if normal ranges are available abnormalities will be flagged. A separate listing is provided presenting all parameters in a subject with any abnormal values. Summary statistics will be provided by treatment and visit/time.

#### **Adverse events**

All information obtained on adverse events will be displayed by treatment and subject. The number and percentage of subjects with adverse events will be tabulated by body system and preferred term with a breakdown by treatment. A subject with multiple adverse events within a body system is only counted once towards the total of this body system and treatment.

## **Immunogenicity**

All immunogenicity results will be listed by subject and visit/time.

### **7.1.3 Graphical presentation**

Boxplots to visualize trends in longitudinal safety data (vitals, ECG, lab parameter) will be created.

## **8 Statistical methods for Biomarker data**

Corporate Confidential Information

Corporate Confidential Information

